ORO monitors intramural research studies to ensure compliance with GCP, organizational policies and regulations. Audit frequency is determined by the IRPAC SOP based on the study level of risk. Results of ORO audits are provided to the PI, The Clinical Director and the IRB.

This study will undergo audits at least once every three years and for cause.

17. Adverse Event Reporting:

Reportable events for this protocol will be tracked and reported in compliance with Policy 801.

18. Alternatives to Participation:

For healthy volunteers, no treatment is provided in this study, and these subjects will not forego any treatment in order to participate in this study. For these subjects, therefore, the alternative is not to participate.

For patients, the treatment provided in this study is the same as the treatment that can be obtained in the community. Therefore, for these subjects the alternative is to receive treatment in the community.

19. Privacy:

All research activities will be conducted in as private a setting as possible.

20. Confidentiality:

Every necessary step will be taken to prevent identification of study participants or violations of confidentiality of the data. Information will be stored using a confidential code wherever possible and data will be treated only as groups. Data on clinical status will be stored in CTDB, and data related to pathophysiology collected as part of this protocol will be stored in the Neuroinformatics Database (NiDB) (http://nidb.sourceforge.net). Of note, to properly link data between CTDB and NiDB it will be necessary to include data for the name, sex, and date-of-birth of subjects both in CTDB and NiDB. However, the plan for maintaining confidentiality in each of these databases has been reviewed with [name] from the Information Resource and Technology Management Branch, and he has determined that procedures for data storage meet NIH security standards. Access will be restricted to approved investigators and staff, and we will utilize the same protections currently in place for CTDB. All data entered into the NIH CTDB will appear only in coded form, though, when necessary, subject identity will be available to appropriate staff. The coded data entered into the NIH CTDB will also be transferred and stored in The Neuroinformatics Database. However, members of the research team and their associate investigators will

have access to these coded data and to information linking coded data to information about specific individuals.

Beyond the procedures noted above, all other information will be stored using a confidential case number, and no identifiers (name, address, phone number, etc.). Thus, unless personnel have access to these identifiers encrypted in the data base, it will not be possible to directly link CTDB information and The Neuroinformatics Database information to individual subjects. Where temporary linking of information with identifiers is needed, such identifiers will be temporarily attached to the data, and will be removed after information has been encoded. Information will be stored using only a confidential code whenever possible, and data will be treated only as groups. All data entered into CTDB will appear only in coded form. Members of the research team will have access to these coded data. Only staff directly involved in the care of each subject or who need to confirm the identity of subjects containing data within different databases will have access to documents that contain identifying information. This will include research staff, clinical staff, and the study psychiatrist.

Secure laptops will be provided to subjects for the attention retraining sessions. These laptops will not be used to collect personally-identifying information and will not contain any personally-identifying information. Subjects will not be able to use the laptops to access NIH networks. The laptops will be encrypted and will have a general user account that only permits the user to execute programs. The Internet will be locked out until the laptop returns to the NIH. All games will be removed from the laptops and no such software will be able to be installed.

We are planning to use 6-8 laptops for this project. Although we cannot predict how many laptops will be used at home by the subjects at a given time, at most, 6-8 laptops will be in use for the purposes of this study. During the course of the project, the subjects will be visiting the NIH on a weekly basis to participate in CBT treatment. If a subject is discontinuing CBT treatment before the end of the eight week period, the laptop will no longer be sent home with the subject. We will follow standard NIH policies with regards to a lost or missing laptop. We will instruct subjects on these policies and ask subjects to notify us immediately if the computer is lost or stolen.

Before each subject is sent home with a laptop, the machine will be cleaned of any residual data. Therefore, any data that is collected during the course of the study will correspond to the current subject that is participating. The subject will receive a unique de-identifiable login. The subject will run an executable file that will save data to the hard drive according to another unique de-identified subject code. The data will be retrieved by a member of the research team each week at their regularly scheduled CBT treatment sessions.

In using the online data collection for the DAWBA, our procedures minimize the risks to patient confidentiality in the following ways:

- 1. No personally identifiable information (PII) is collected. Patients and their parents/guardians are explicitly instructed not to use any such information when answering questions.
- 2. Only our team at the NIMH, but not the web team or any other party, can identify the person providing the information or who the information concerns. The only people with access to the key that links the patient name with the password provided to the patient are in our lab group. That key is stored on our secure server at NIH.
- 3. The website on which the data are collected is secure and has been used successfully around the world to collect such data, including in Scandinavian countries with strict regulations on patient confidentiality commensurate to the ones applied by the NIH. It has passed the Privary Impact Assessment (TPWA-PIA) by our ISSO, [name], at NIH.

- 4. The founders and owners of the website, [name] and [name] have an established track record with this method of data collection and enjoy a worldwide reputation for top academic work and commitment to confidentiality through IT applications. They have worked with a number of governments around the world, are known to our group, and are long-time trusted collaborators with [name] prior to his coming to NIH.
- 5. DAWBA forms that have not been downloaded to our server, and thereby removed, will be purged from the web application within two months of their completion.

21. Conflict of Interest:

None

22. Technology Transfer:

None.

23. Research and Travel Compensation:

All families will receive reimbursement based on NIH standards for time devoted to the research project. Patients will not receive reimbursement for participation in the treatment study, but they will be compensated for participation in other non-therapeutic aspects of this study at the same rate at which volunteers will be compensated. Hence, both patients and volunteers will receive reimbursement for participation in the neuropsychological, psychophysiological, MEG and fMRI procedures. This compensated for their time for each procedure.

Payment Schedule: Subjects will be compensated based on the schedule shown below. This compensation will be provided for each of the times that the subject completes the procedure, though compensation for the psychiatric assessment will only be provided at the initial assessment. Therefore, families of children/youth who complete all phases of this study will receive up to \$940, depending on whether computer tasks, MEG scans, and fMRI procedures are completed twice. Adult patient participants receiving open treatment will be reimbursed \$320. Additional compensation is provided if monetary tasks are completed. In this protocol there are tasks that pay participants based on their winnings. The three reward tasks from work by Averbach (Shopping, Novelty, Horizons), Affective Posner 2, MID, and PRR pay participants up to \$ 25 (for each task) more than the amount for just performing the task; the extra amount is based on their winnings during that task. The total amount of winnings from all these tasks (whether outside or inside the MRI scanner) that any participant can receive will not exceed \$300.

Of note, participation is lower for follow-up relative to baseline measures. One set of follow-up measures includes measures of symptoms assessed through questionnaire. This to generates measures of symptoms other than our primary outcome measures for our clinical trials. The other set of follow-up measures includes measures of brain function, to quantify post-treatment changes in biomarkers through imaging.

Based on communication with healthy subjects, at baseline, it appears as if this group of subjects works to arrange their study participation at a time in their yearly schedule where the subjects are relatively free to participate in research. Six to 10 weeks later, when follow-up measures are sought, it appears as if the schedules of many healthy subjects have change, making the follow-up assessments less convenient. Similar changes appear to occur in patients, based on communication with this group. Moreover, at follow-up assessments, patients typically are much improved in terms of their symptoms. As a result, not only are follow-up tests less convenient, but they also come at a time when motivation for participation might

diminish. We add a \$100 bonus to be paid after the follow-up assessments are completed, after the followup imaging session. Employees and staff who participate during work hours must have permission from their supervisor. NIH employees and staff must either participate outside of work hours or take leave in order to receive compensation.

Task	Total \$\$	Notes
	As of June	
	2022	
History	\$15	
Phlebotomy	\$15	
Cheek swabs	\$8	
Initial K-SAD	\$30	•
KSADS (Repeat)/SCID	\$8	•
Questionnaires	\$30	Ex: Demographics, CCC, SRC, MASC
Ratings	\$30	Such as the sum of PARs, CDRS, YMRS, BPRS,
		etc
Six-Month Follow Up Interview and Forms	\$30	Ex: PARs
Ecological Momentary Assessment (EMA) - Study 1	\$90	Subjects will receive \$90 for each time that they return the phone and an additional \$10 for responding to 75% of questions. This will be completed three times.
Ecological Momentary Assessment (EMA) – COVID-19 Study	\$120	Subjects will receive \$20 for a retraining of the EMA protocol, \$90 for completing the session, and an addition \$10 for responding to 75% of the questions.
Neuropsychological Testing	\$40	
WASI only	\$15	
Computer Tasks (no winnings) (in-person and mobile)	\$15-30	This is given upon the completion of tasks. Payment varies depending on task length (for tasks with monetary incentives, see below)
Computer Tasks (with winnings) (in-person and mobile)	\$60	Subjects will receive \$40 for completing the task. Extra amount up to \$20 based on winnings,
Mobile App Task	\$40	Subjects will receive \$20 per play, with the opportunity to play twice for a maximum of \$40.
Psychophysiology	\$15	
Conditioning Experiment (in-person and mobile)	\$100	
Heat Pain Task	\$100	
Memory Task (in-person and mobile)	\$30	
Confidence Task (in-person and mobile)	\$10	Extra amount up to \$20, based on winnings
Risk and Ambiguity Task (in-person and mobile)	\$10	Extra amount up to \$100, based on winnings
MID/Knutson (fMRI & behavioral)	W (1 run)	W= 1 run, which subjects randomly pick at the end (subjects should not receive money from the practice run)
WOF	W (1 run)	
PD (behavioral & fMRI)	W (1 run)	W = 1 of 4 runs, which is randomly selected at the end
Eye Tracking (behavioral & fMRI)		
Antisaccade Task	W (1 run)	W= 1 run, which subjects randomly pick at the end
	W (cum)	, , , , , ,

Saccade Task		W=cumulative winnings	
		* pay a minimum of \$15 for winnings (as of 7/`4/05) * pay a minimum of \$30 for tasks at or exceeding 30 minutes (as of 2/13/19)	
Σ winnings < \$150			
If monetary tasks are completed within a 1 month period, the maximum earnings for each subject is \$150. If the time			
interval between each task is greater than 1 month, do not add the previous gains on monetary task to winnings.			
Functional MRI	\$130	Subjects participating in the University of	
•	+ W (1 run)	Wisconsin-Madison research project will be	
Task: Winnings		compensated for extended time in scanning suite	
Task: Extended time	\$250	for fMRI.	
Structural MRI	\$40		
M/EEG scan	\$130	Extra amount up to \$25, based on winnings	
Completion Bonus	\$100		
Escort Fee*	\$20	Given at the request of parent/discretion of IRTA for	
		family in need, baby-sitting, etc.	
Travel Fee	\$0.58/mile	Participants will be reimbursed \$0.58 per mile for	
		travel by bus, train, or taxi to the NIH.	

In regard to total possible compensation, we have summed payments across all research activities, including behavioral tasks and scans, considering all possible repetitions. We have determined that the maximum possible compensation for child participants is \$2500 and \$1000 for adult participants. This has been clarified in section 23 of the protocol.

24. References:

- 1. Alpert, J.E., et al., *Childhood psychopathology retrospectively assessed among adults with early onset major depression.* Journal of Affective Disorders, 1994. **31**(3): p. 165-171.
- 2. Battaglia, M., et al., *Age at onset of panic disorder: Influence of familial liability to the disease and of childhood separation anxiety disorder.* The American Journal of Psychiatry, 1995. **152**(9): p. 1362-1364.

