4.1. Associations among pediatric and adult mood/anxiety disorders

4.1.1. Comorbidity: Most children with an anxiety disorder suffer from multiple disorders^{1, 4, 5, 7-9}. Comorbidity is particularly strong among social phobia, separation anxiety, and generalized anxiety disorders.⁴ Such comorbidity complicates studies on risk factors and treatments. As a result, most current treatment and risk factor research on childhood anxiety disorders groups together the diagnoses of social phobia, separation anxiety disorder, and generalized anxiety disorders.^{1, 3-5, 7-9, 48} In fact, virtually all treatment trials combine the three diagnoses into a single category.^{5, 48} The current protocol will combine these three conditions into one anxiety group. There also is considerable comorbidity between childhood anxiety and depressive disorders. This further complicates studies on disorder-specific correlates. The current protocol compares healthy youth with two patient groups: i) youth with any one of three anxiety disorders (social phobia, separation anxiety disorder, and generalized anxiety disorder) in the absence of depression; and ii) youth with depression, with or without anxiety. Sub-analyses also will contrast depressed subjects with and without anxiety disorders and subjects with specific anxiety disorders.

4.1.2. Associations Between Disorders in Children and Adults: Youth with mood or anxiety disorders face a two-to-five fold increased risk for adult depressive and anxiety disorders.¹⁻¹¹ In fact, most adults with a mood or anxiety disorder had shown previous signs of a mood or anxiety disorder during childhood.^{1, 4, 5, 8} Youth with various mood and anxiety disorders also show high familial loading for mood and anxiety disorders.^{2, 6, 10, 11} Parental history of a mood or anxiety disorder may represent the most potent risk factors for personal history of a disorder in a child.⁷ Based on such data, recent studies on pathophysiology of adult mood and anxiety disorders provide insights on pathophysiology in pediatric conditions.

4.2. *Cognitive processes and brain circuitry in adults:* Mood and anxiety disorders are associated with cognitive abnormalities that may result from disruptions in neural circuits regulating attention and memory.

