A total of 360 juvenile subjects will be studied comprehensively, comprising groups of "healthy," "anxious," and "depressed" youth. Of note, we anticipate enrolling far more than 360 subjects (see accrual numbers; total accrual ceiling is set to be n=2530), as not all subjects enter all phases of the study. For example, some subjects may remit during the initial pre-treatment phases of the study. Such subjects will, of course, not receive treatment. Other subjects may only tolerate a portion of the procedures proposed here. By "studied comprehensively", we mean that we plan to obtain data for *each* key assessment measure in a total of 360 juveniles, as stratified below.

Based on prior studies, 80% of the depressed subjects are expected to meet criteria for a current anxiety disorder. Thus, our goal is to collect data for each measure among 20 depressed adolescents without an anxiety disorder as well as 40 depressed adolescents with a comorbid anxiety disorder. In terms of anxiety disorders, we expect to study on each of our tasks approximately 80 subjects with social phobia, 40 subjects with separation anxiety disorder, and 80 subjects with generalized anxiety disorder. These numbers exceed n=150 due to comorbidities. Of note, we plan to directly contrast specific anxiety disorders, particularly generalized and social anxiety disorders. Thus, a relatively large sample size is needed.

Hypotheses for studies in adult mood and anxiety disorders are identical to those in youth. Moreover, we expect comparable effect sizes for between-group comparisons of healthy and impaired adults as found in healthy and impaired adolescents. As a result, we will study 60 adults with anxiety disorders, of whom approximately 30 will have social phobia; 30 will have generalized anxiety disorder; and 20 will have panic disorder. This will provide sufficient data for power analyses in specific anxiety disorders.

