Prior to open-access sharing via web- based repository, all datasets will be further de-identified and anonymized by the removal of face information from the image to prevent any inappropriate reconstruction of the image that could lead to identification of a participant. Further, each individual participant's dataset will be assigned a randomized five-digit participant identifier, along with a site identifier (two letters which map to the site providing the data). The relationship between the anonymized code and the original subject ID will be destroyed so as to assure that the dataset will be truly anonymized. For each dataset, demographic information provided via web-archive will be limited to (when available): age (18 and up), gender (male, female) and handedness. This information will serve to facilitate more careful characterization of the data, without entailing risk of violation of confidentiality.

11.5. Sample Size Justification:

Determination of sample sizes is based on the primary goals of this protocol, to document neuro-cognitive differences between patients and healthy groups on neuropsychological and fMRI tasks. Sample size determinations are not informed by hypotheses on treatment effects. This derives from two factors. First, it is impossible to determine sample sizes for these contrasts, as they depend partly on the treatment choices of families and on the treatment response rates of subjects. Second, these contrasts must assume that pre-treatment differences in neuro-cognitive and fMRI parameters differ between patients and comparisons. Given the paucity of prior work, this is a somewhat tenuous assumption.

Power calculations assume sample sizes of n=45 for each contrast. This includes groups with specific anxiety disorders, and it includes studies that separately consider adults or youth. Of note, for studies of major depression, the sample size will be larger (n=60) when considering all depressed subjects as a group, either among youths or among adults. However, sample sizes are expected to be smaller for subjects with depression, sub-divided based on the presence or absence of an anxiety disorder (n=30 for each, in adults and in youth).

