With sample sizes of n=45, statistical power is adequate (β >0.80) for detecting differences between patients and comparisons, assuming medium-to-large effects (standardized difference [*d*]=0.8-1.2).⁹⁶ Such effect sizes have typically emerged in prior studies documenting hypothesized between-group differences in psychological function or fMRI activation. This includes prior studies in both adults and in youths. Moreover, we expect to see similar differences in youths and adults, and our prior studies in both groups find between-group differences of this magnitude. Thus power will be adequate to test all of our primary hypotheses concerning both fMRI and neuro-cognitive differences between patient groups and healthy adolescents as well as our secondary hypotheses on comparable differences in adults. For any comparison where a cell contains less than 45 subjects (e.g. subjects with major depression but not an anxiety disorder), power will be less than adequate. These data will be used to generate estimates of effect sizes to consider the feasibility of conducting further studies in such relatively select subject groups. Finally, for treatment effects, based on prior work in this protocol, we expect a medium effect separating patients receiving CBT randomized to active and placebo forms of treatment. Therefore, the plan is to include 120 subjects in the RCT, with 60 randomized to the active form of ABMT and 60 randomized to the placebo form of ABMT.

12. Human Subjects Protection:

12.1. Subject Selection:

This study examines brain structure and function in psychiatrically healthy as well as clinically anxious or depressed children, adolescents and adults. For healthy subjects, volunteers will be solicited, as prior studies performed at the NIH on developmental aspects of brain structure document the feasibility of this approach.^{97, 98} Impaired subjects will be recruited when they present for treatment. Sample sizes for the current project derive from power considerations in the proposed fMRI and treatment studies. In general, power in the proposed fMRI studies will be adequate to detect large effect sizes with n=15. Assuming that acceptable data will be generated from approximately 90% of studies, the proposed sample size will allow us to obtain data in 15 subjects for each relevant group of subjects.

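### Section 11.5's n=45 does not match the group sizes planned in 6.1, and its under-45 rule does not follow from the stated inputs for patient-versus-healthy contrasts

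*Combined protocol and SAP*

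**What the plan says.** Section 11.5 sets one planning size: "Power calculations assume sample sizes of n=45 for each contrast. This includes groups with specific anxiety disorders". It applies this to adults and youth considered separately. It makes exceptions only for depression: 60 for all depressed subjects, in youths or in adults, and 30 in each half when they are split by presence of an anxiety disorder. It gives d=0.8-1.2 and power above 0.80 (printed as β) for patients against comparisons. It then adds a rule, beginning "For any comparison where a cell contains less than 45 subjects", under which power is inadequate and the data serve to estimate effect sizes for later studies. No alpha appears in 11.5; two-tailed 0.05 is given in 11.2.1.2.

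Section 6.1 gives the planned cells. For youth with anxiety: "approximately 80 subjects with social phobia, 40 subjects with separation anxiety disorder, and 80 subjects with generalized anxiety disorder", with the remark "These numbers exceed n=150 due to comorbidities". For the 60 adults with anxiety: "approximately 30 will have social phobia; 30 will have generalized anxiety disorder; and 20 will have panic disorder", followed by "This will provide sufficient data for power analyses in specific anxiety disorders". Depressed youth are 40 with and 20 without an anxiety disorder. Section 6.1 and the Precis plan 100 depressed adults.

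Patient-versus-patient contrasts are also planned. Section 4.1.1, on the youth groups, says "Sub-analyses also will contrast depressed subjects with and without anxiety disorders and subjects with specific anxiety disorders". The youth paragraph of 6.1 says "we plan to directly contrast specific anxiety disorders, particularly generalized and social anxiety disorders".

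**The concern.** The size that 11.5 says was used in the power calculations is not the size planned for most of the diagnosis groups it names. Under 11.5's own rule, four of the six diagnosis cells in 6.1, including every adult one, would become effect-size estimation only. Yet the sentence that introduces n=45 lists the specific anxiety disorders as covered.

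The rule decides which contrasts count as hypothesis tests and which as feasibility data. If 45 is not where power falls below 0.80 under the stated assumptions, planned contrasts could be set aside without cause. And a single cut-off for both patient-versus-healthy and patient-versus-patient contrasts hides the cases where power really is marginal.

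**Working it through.** **Group sizes side by side**

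| Group | 11.5 | 6.1 / Precis |
|---|---|---|
| Youth social phobia / separation anxiety / GAD | 45 each | 80 / 40 / 80 |
| Adult social phobia / GAD / panic | 45 each | 30 / 30 / 20 |
| Depressed youth with / without anxiety | 30 / 30 | 40 / 20 |
| All depressed adults | 60 | 100 |
| Healthy adults | not given | 150 (Precis), 650 (6.1) |

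Section 6.1 also refers to 120 adults after listing 100 + 60 = 160. It expects 80% of depressed youth to have an anxiety disorder, but 40/60 = 67%.

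**Inputs for power.** d=0.8, the low end of 11.5's range; two-sided alpha 0.05, carried over from 11.2.1.2; 150 healthy comparators, from the Precis.

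**Formula.** Two-sample t-test with noncentrality d·√(n1·n2/(n1+n2)) on n1+n2−2 degrees of freedom.

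**The plan's own figure.** 45 vs 45 at d=0.8: noncentrality 0.8·√(2025/90) = 3.79, critical value 1.99, power 0.964. The claim of more than 0.80 is reproduced.

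**Where 80% is reached.** With equal groups at d=0.8, 25 per group gives 0.79 and 26 gives 0.807. At d=1.2, 12 per group suffices.

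**Patient versus 150 healthy**

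| Patients | Noncentrality at d=0.8 | Power at d=0.8 | Detectable d at 80% power |
|---|---|---|---|
| 20 | 3.36 | 0.916 | 0.67 |
| 30 | 4.00 | 0.978 | 0.56 |
| 40 | 4.50 | 0.994 | 0.50 |
| 60 | 5.24 | 0.999 | 0.43 |

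With only 45 healthy comparators, 20 patients still give 0.834. With 650 healthy adults, 20 and 30 patients give 0.94 and 0.99.

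**What would make about 45 the threshold**
- d of about 0.6 with equal groups: 45 vs 45 gives 0.804.
- d of about 0.5 against 150 healthy: 20, 30, 40 and 45 patients give 0.55, 0.70, 0.798 and 0.83.
- Alpha of about 0.004 at d=0.8 with equal groups: 45 vs 45 gives 0.80. At that alpha against 150 healthy, 20, 30 and 40 give 0.68, 0.86 and 0.94, so only n=20 falls short.

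None of these is stated.

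**Patient versus patient at d=0.8, cells treated as non-overlapping**

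| Cells | Power | Detectable d at 80% power |
|---|---|---|
| 20 vs 40 (depressed youth, 6.1 split) | 0.82 | 0.78 |
| 30 vs 30 | 0.86 | 0.74 |
| 40 vs 80 | 0.98 | 0.55 |
| 80 vs 80 | 0.999 | 0.45 |

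Diagnoses overlap: 30+30+20 = 80 diagnoses in 60 adults, and 80+40+80 = 200 in 150 youth. The diagnosis rows are therefore upper bounds if subjects with both diagnoses are left out. For illustration, if 10 adults had both social phobia and GAD, 30 vs 30 would become 20 vs 20, with power 0.69.

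**The case against.** The rule errs on the safe side. It claims less for small cells than it could, so no false claim of power results, and the one power figure in 11.5 is correct. That stands, and it limits the harm. But a rule that moves planned contrasts out of hypothesis testing still needs a basis.

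Section 11.5 describes the effects as medium-to-large. If medium is taken as d=0.5 (an assumption; the documents do not define the term), the rule roughly holds against 150 healthy subjects. However, 11.5 attaches d=0.8-1.2 to that phrase. If a smaller effect was meant, it should be stated. The choice of 150 comparators is likewise not written in 11.5, but 20 patients against 45 already exceed 0.80.

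Some stronger readings are tempting, and the documents do not support them:
- A reader might infer that 6.1 declares the adult diagnosis cells adequately powered. Its words are "This will provide sufficient data for power analyses in specific anxiety disorders", which can mean data from which power can be worked out. That fits 11.5's use of small cells for effect-size estimates.
- A reader might cite 20 vs 30 (adult panic against social phobia or GAD, power 0.775) as an underpowered planned contrast. Neither 4.1.1 nor 6.1 names it; their statements on contrasting disorders concern youth.
- A reader might cut the 20 vs 40 contrast by 10% for unusable scans, giving 0.78. Section 6.1 frames these numbers as data to be collected on each measure, so the loss is probably already allowed for.
- A reader might set the 15 per group in 12.1 against n=45. It agrees with 11.2.1.2 (15 vs 15 at d=1.2 gives 0.89) and is not an upper limit. It needs wording alignment only.

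**Conclusion.** The concern holds within limits. The n=45 in 11.5 disagrees with 6.1 for all six diagnosis cells, four of them below 45, and the depression figures disagree for adults (60 versus 100) and for the youth split (30/30 versus 40/20). For patient-versus-healthy contrasts, the under-45 rule does not follow from d=0.8-1.2 at two-sided 0.05: every planned cell below 45 has power of at least 0.92 against 150 healthy subjects. For patient-versus-patient contrasts no single cut-off works, because power depends on both cells and on diagnostic overlap.

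This rests on carrying alpha over from 11.2.1.2, on d=0.8 as the planning effect, and on 150 healthy comparators. The primary youth contrasts (150 anxious and 60 depressed against 150 healthy) are unaffected. The problem is confined to diagnosis-specific, depression-subgroup and secondary adult contrasts. It should be corrected, but it does not threaten the main aim.

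**What to change.** In 11.5:
- State alpha, and the effect size and allocation that justify any threshold.
- Replace the uniform n=45 and the under-45 rule with a short table of 6.1's cell sizes against the planned healthy group, giving power at d=0.8 and the detectable d at 80% power.
- Show patient-versus-patient contrasts separately, using non-overlapping cell sizes.

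In 6.1 and 11.5 together:
- Use one depressed-adult total and one depressed-youth split, consistent with the comorbidity rate quoted.
- Use one healthy-adult comparator number (150 or 650).
- Correct the 120 adults (100 + 60 = 160).

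Align the n=15 sentence in 12.1 with the planned group sizes as a minor wording change. The cost is protocol wording and one table, with no change in enrolment.
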